5.5.2.1.1. Analyses Related to IGA

5.5.2.1.1.1. Through Week 16

- The proportion of IGA responses (IGA score of cleared [0]; an IGA score of cleared [0] or minimal [1]; and an IGA score of mild or better [≤ 2]) will be summarized over time through Week 16 by treatment group. Line plots will be provided displaying the proportions and exact 95% CIs of subjects achieving an IGA score of 0; and an IGA score of 0/1 through Week 16.
- The proportion of IGA responses (IGA score of cleared [0]; an IGA score of cleared [0] or minimal [1]; and an IGA score of mild or better [≤ 2]) will be summarized over time through Week 16 by treatment group using observed data after applying treatment failure rules and rescue treatment rules.

5.5.2.1.1.2. From Week 16 through Week 52

PASI 90 responders at Week 16 (after withdrawal of guselkumab)

- To evaluate the efficacy of the maintenance therapy, the proportion of IGA responses (IGA score of cleared [0]; an IGA score of cleared [0] or minimal [1]; and an IGA score of mild or better [≤ 2]) will be summarized over time through Week 52 for subjects randomized to the guselkumab group who were PASI 90 responders at Week 16. Non-responder status will be assigned after retreatment of guselkumab.

PASI 90 responders at Week 16 (after retreatment of guselkumab)

- IGA scores at the time of retreatment of guselkumab and the proportion of retreated participants who achieve an IGA score of cleared (0), an IGA score of cleared (0) or minimal (1), and an IGA score of mild or better (≤ 2) over time (eg, 4 weeks after retreatment, 8 weeks after retreatment, 12 weeks after retreatment) following the retreatment of guselkumab will be summarized for subjects randomized to the guselkumab group who were PASI 90 responders at Week 16.

PASI 90 non-responders at Week 16

- The proportion of IGA responses (IGA score of cleared [0]; an IGA score of cleared [0] or minimal [1]; and an IGA score of mild or better [≤ 2]) will be summarized over time through Week 52 by treatment group.

5.5.2.1.2. Analyses Related to PASI

5.5.2.1.2.1. Through Week 16

- The proportion of participants who achieve a PASI 50 response at Week 16 will be compared between the guselkumab group and the placebo group using Fisher's exact test stratified by region and age. The differences in proportions with exact 95% confidence intervals will be presented.
- The percent improvement from baseline in PASI at Week 16 will be compared between the guselkumab group and the placebo group using a using Wilcoxon rank-sum test.
- The percent improvement from baseline in PASI will be summarized over time through Week 16 by treatment group.
- The proportion of PASI responses (PASI 50, 75, 90, and 100) will be summarized over time through Week 16 by treatment group. Line plots will be provided displaying proportions and exact 95% CIs of PASI 100 responders and PASI 90 responders through Week 16.
- The proportion of PASI responses (PASI 50, 75, 90, and 100) will be summarized over time through Week 16 by treatment group using observed data after applying treatment failure rules and rescue treatment rules.
- The proportion of subjects who achieve 100% improvement, $\geq 90\%$, $\geq 75\%$, or $\geq 50\%$ improvement from baseline in PASI component (induration, erythema, and scaling) and region component (head, trunk, upper extremities, and lower extremities) will be summarized at Week 16 by treatment group.

5.5.2.1.2.2. From Week 16 through Week 52

PASI 90 responders at Week 16 (after withdrawal of guselkumab)

- The time to loss of PASI 90 response after withdrawal will be summarized for participants randomized to the guselkumab group who were PASI 90 responders at Week 16. The percent of subjects who maintained a PASI 90 response from Week 20 through Week 52 will be estimated from life-table methodology and a survival curve (probability that participants maintain PASI 90 response after withdrawn) will be presented.

- The duration of PASI 90 response will be summarized using life-table methodology for participants randomized to the guselkumab group who were PASI 90 responders at Week 16. The estimated number of weeks at which 90%, 75%, 50% and 25% of subjects maintained a PASI 90 response will be provided.
- The time to loss of 50% of the Week 16 PASI improvement (ie, time to retreatment) after withdrawal will be summarized for participants randomized to guselkumab group. The percent of subjects who experienced loss of 50% of Week 16 PASI improvement from Week 20 through Week 52 will be estimated from life-table methodology and cumulative incidence of loss of 50% of Week 16 PASI improvement curve will be presented.
- The time to loss of 50% of Week 16 PASI improvement will be summarized using life-table methodology for participants randomized to the guselkumab group who were PASI 90 responders at Week 16. The estimated number of weeks at which 90%, 75%, 50% and 25% of subjects experienced loss of 50% of Week 16 PASI improvement will be provided.
- The proportion of PASI responses (PASI 50, 75, 90, and 100) will be summarized over time through Week 52 for subjects randomized to the guselkumab group who were PASI 90 responders at Week 16. Non-responder status will be assigned after retreatment of guselkumab.
- The percent improvement from baseline in PASI will be summarized over time through Week 52 for subjects randomized to the guselkumab group who were PASI 90 responders at Week 16. PASI score at the time of retreatment will be carried forward after retreatment of guselkumab through Week 52.

PASI 90 responders at Week 16 (after retreatment of guselkumab)

- PASI score and PASI percent improvement at the time of retreatment with guselkumab will be summarized for subjects randomized to the guselkumab group who experienced loss of 50% of Week 16 PASI improvement.
- The PASI responses (PASI 50, 75, 90 and 100) with respect to baseline will be summarized over time (eg, 4 weeks after retreatment, 8 weeks after retreatment, 12 weeks after retreatment) following retreatment with guselkumab.

PASI 90 non-responders at Week 16

- The proportion of PASI responses (PASI 50, 75, 90, and 100) will be summarized over time through Week 52 by treatment group.

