#### **9.4.1.5. Other Secondary Analyses**

In addition to the primary and major secondary analyses, the analyses for other efficacy endpoints will be performed and nominal p-values will be provided. The Fisher's exact test, stratified by age and region, will be used to compare the proportion of participants responding to treatment. Continuous response parameters will be compared using an MMRM analysis or an ANCOVA model, adjusting for baseline value, age, and region. Life table estimates will be provided for the time to event variables. All statistical testing will be performed at 2-sided ( $\alpha=0.05$ ). The other secondary analyses are:

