#### **Secondary Analyses for Participants Randomized in Part 1**

- The proportion of retreated participants that achieve a PASI 90 response over time after retreatment will be summarized.
- The proportion of retreated participants that achieve PASI responses (PASI 50, 75, 90, and 100) or IGA responses (IGA of cleared [0], minimal [1], or mild [2], IGA of cleared [0] or minimal [1], and IGA of cleared [0]) over time after retreatment will be summarized.
- The time to loss of 50% of the Week 16 PASI improvement (ie, time to retreatment) after withdrawal will be summarized for participants randomized to guselkumab group.
- The time to loss of PASI 90 response after withdrawal will be summarized for participants randomized to guselkumab group.
- The proportion of participants who achieve a PASI 50 response at Week 16 will be compared between the guselkumab group and the placebo group.
- The proportion of participants who achieve an IGA score of mild or better ( $\leq 2$ ) at Week 16 will be compared between the guselkumab group and the placebo group.

- The percent improvement from baseline in PASI will be summarized over time through Week 16.
- The proportion of PASI responses (PASI 50, 75, 90, and 100) will be summarized over time through Week 16.
- The proportion of IGA responses (IGA of cleared [0], minimal [1], or mild [2], IGA of cleared [0] or minimal [1], and IGA of cleared [0]) will be summarized over time through Week 16.
- The proportion of participants with CDLQI=0 or 1 at Week 16 will be compared between the guselkumab group and the placebo group among randomized participants with a baseline CDLQI>1.
- Body surface area involved (BSA) and change from baseline in BSA at Week 16 will be compared between the guselkumab group and the placebo group.
- BSA and change from baseline in BSA will be summarized over time through Week 16.
- The proportion of participants with FDLQI=0 or 1 at Week 16 will be compared between the guselkumab group and the placebo group among randomized participants with a baseline FDLQI>1.
- The change from baseline in FDLQI at Week 16 will be compared between the guselkumab group and the placebo group.

In addition, relevant comparisons at Week 16 will also be conducted between the etanercept group and the placebo group.

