5. EFFICACY

Unless otherwise stated, efficacy data summaries will be provided for the full analysis set for each part. The Fisher's exact test, stratified by age group and region, will be used to compare the proportion of subjects responding to treatment if appropriate. Continuous response parameters (i.e. change from baseline in CDLQI) will be compared using Mixed Model Repeat Measurement (MMRM) analysis with factors of treatment, region, age group, baseline, visit, baseline by visit and treatment by visit; or an analysis of covariance (ANCOVA) model, adjusting for baseline value, age group, and region. If the normality assumption is violated, non-parametric methods will be used as appropriate. All statistical testing will be performed at a 2-sided significance level of 0.05.

Descriptive statistics, such as mean, median, standard deviation, minimum and maximum, interquartile range for continuous variables, and counts and percentages for categorical variables will be used to summarize the data. Life table estimates will be provided for the time to event variables. Graphical data displays and subject listings may also be used to summarize the data.

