5.1.3.3. Treatment Failure Rules

A subject who meets one or more treatment failure criteria specified in Section 5.1.3.2 will be considered a treatment failure from that point onward. The baseline values will be used for all directly measured endpoints regardless of the actual measurements. Zero will be assigned to improvement and percent improvement, and non-responder status will be assigned to binary response variables.

Treatment failure is assumed to have occurred at the earlier of the following dates:

- Date of discontinuation (DC) of study treatment due to lack of efficacy or
- Date of discontinuation of study agent due to an AE of worsening of psoriasis or
- Start date of a protocol-prohibited medication/therapy during the study that could improve psoriasis

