5.1.3.6. Missing Data Imputation

After the treatment failures and rescue treatment rules are applied, the remaining missing data will be handled as follows for all of the efficacy analyses including the analyses at key visits (eg Week 16) and over time through Week 52:

- Non-responder imputation will be applied for binary efficacy endpoints.
- No imputation will be performed for missing post baseline continuous values. The statistical model (ie, MMRM) will adjust for missing data.

For the analyses related to the time to event endpoints during the withdrawal and retreatment period, missing PASI score after the Week 16 visit will not be imputed and the value will remain as missing after applying treatment failure rules.

For the efficacy analyses that evaluate the efficacy of retreatment or initiation of guselkumab, after the treatment failure rules are applied, no imputation will be performed for missing data following the retreatment or initiation of guselkumab.

For the efficacy analyses through LTE period, no treatment failures and no missing data imputation will be performed, and the analyses will be based on observed data.

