5.5.2. Analysis Methods

5.5.2.1. Secondary Analyses for Participants Randomized in Part 1

For Part 1, the other secondary efficacy analyses described in this section below will be based on the full analysis set combining subjects from Part 1a and Part 1b. All statistical testing will be performed at the 2-sided 0.05 significance level. Nominal p-values will be presented. The Fisher's exact test, stratified by age and region, will be used to compare the proportion of participants responding to treatment. Continuous response parameters will be compared using an MMRM analysis with fixed factors of treatment, baseline value, age, region, visit, treatment by visit and baseline by visit interaction terms. Life table estimates will be provided for the time to event variables. Subjects who meet loss of response criteria (eg, loss of PASI 90 response, loss of 50% Week 16 PASI improvement) will be considered an 'Event'. Subjects who did not meet the criteria for loss of response at Week 52 will be censored.

In addition, for the analyses related to patient reported outcomes (CDLQI and FDLQI), only subjects with baseline measurements will be included.

The analyses of other secondary efficacy analyses outlined in the following sections in general will be carried out for 2 periods.

Analyses through Week 16 (placebo controlled period)

Efficacy analyses at Week 16 and over time through Week 16 will be summarized by randomized treatment group at Week 0

- **Placebo:** subjects randomized to placebo group at Week 0
- **Guselkumab:** subjects randomized to guselkumab treatment group at Week 0
- **Etanercept:** subjects randomized to etanercept treatment group at Week 0

Analyses from Week 16 to Week 52 (withdrawal and retreatment period)

- Efficacy of PASI 90 responders at Week 16
 - After withdrawal of guselkumab: To evaluate the loss of response after withdrawal of study agent, efficacy analyses will be performed for subjects who were randomized to guselkumab at Week 0, were PASI 90 responders at Week 16 and were withdrawn from study agent after Week 16. Non-responder status will be assigned after retreatment for binary endpoints. The measurement at the time of retreatment will be carried forward after retreatment for continuous endpoints.

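### The Week 16 rank test on PASI percent improvement names no strata, although the allocation ratios tie age group to treatment

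*SAP*

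**What the plan says.** In SAP 5.5.2.1.2.1, PASI percent improvement at Week 16 is "compared between the guselkumab group and the placebo group using a using Wilcoxon rank-sum test". No stratum, covariate, effect estimate or confidence interval is named. The bullet just before it, on PASI 50, compares the same two groups "using Fisher's exact test stratified by region and age" and gives an exact confidence interval for the difference.

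The parent section, SAP 5.5.2.1, sets a general rule for Part 1 other-secondary analyses: "Continuous response parameters will be compared using an MMRM analysis with fixed factors of treatment, baseline value, age, region, visit", plus interactions. The Week 16 comparisons of CDLQI (SAP 5.3.3), FDLQI and BSA (SAP 5.5.2.1.3.1) all use MMRM.

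Four other places bear on the point:

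- SAP section 5 has a conditional fallback: "If the normality assumption is violated, non-parametric methods will be used as appropriate".
- Protocol 9.4.1.5 gives the generic rule: "Continuous response parameters will be compared using an MMRM analysis or an ANCOVA model, adjusting for baseline value, age, and region". Its list entry for this endpoint, however, plans only a summary: "The percent improvement from baseline in PASI will be summarized over time through Week 16".
- SAP 5.1.3.3 covers treatment failures: "Zero will be assigned to improvement and percent improvement". SAP 5.1.3.5 does the same for rescue users through Week 16, and SAP 5.5.3 applies these rules to all Part 1 PASI analyses.
- SAP 5.1.3.6 covers what is still missing: "No imputation will be performed for missing post baseline continuous values. The statistical model (ie, MMRM) will adjust for missing data".

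**The concern.** Part 1a and Part 1b are randomised separately with different ratios and then pooled. The share of adolescents therefore differs between guselkumab and placebo by design, not by chance. If PASI improvement differs by age for any reason other than treatment, an unstratified test attributes part of that difference to the drug. The PASI 50 test and the MMRM comparisons of the other continuous endpoints guard against this; this test does not.

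A smaller issue is missing data. The SAP leaves residual missing continuous values unimputed because the MMRM is expected to deal with them. A rank-sum test at a single visit cannot, so those participants drop out.

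At stake is the only between-group test on the continuous PASI scale. As written it yields a p-value with no effect estimate.

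**Working it through.** **Nearest figure in the plan.** The documents give no power, SD or dropout rate for this endpoint. The nearest stated figure is at least 99% power for each co-primary endpoint (65% vs 13%, n = 40 vs 25, two-sided 0.05; SAP 1.4). An unstratified exact Fisher calculation gives 99.3%, so that figure is reproduced. It does not depend on the point made here.

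**Age imbalance by design** (SAP 1.2):

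| | Guselkumab | Placebo |
|---|---|---|
| Part 1a (12 to <18 years) | 30 | 15 |
| Part 1b (6 to <12 years) | 10 | 10 |
| Adolescent share | 30/40 = 75% | 15/25 = 60% |

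Suppose adolescents improve more than children by d SD whatever they receive. With no drug effect, the group means then differ by (0.75 − 0.60) × d = 0.15d SD. Region is different. Allocation is blocked within region, so leaving region out costs some efficiency but creates no imbalance of this kind.

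**Effect on the error rate.** Assume a normal outcome with SD 1 within each age group and no treatment effect.

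- True standard error of the mean difference, with stratum sizes fixed: √(1/40 + 1/25) = √0.065 = 0.2550.
- Standard error as an unstratified test sees it, because the age spread is counted as noise: √[(1 + 0.75 × 0.25 × d²)/40 + (1 + 0.60 × 0.40 × d²)/25]. This is 0.2619 at d = 0.5 and 0.2816 at d = 1.
- Chance of a significant result favouring guselkumab: P(Z > (1.96 × SE seen − 0.15d)/0.2550).
- Chance of one favouring placebo: the same expression with + 0.15d.

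At d = 0.5: (0.5133 − 0.075)/0.2550 = 1.72, giving 4.3%; (0.5133 + 0.075)/0.2550 = 2.31, giving 1.1%; total 5.3% (from unrounded terms).

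At d = 1: (0.5519 − 0.15)/0.2550 = 1.58, giving 5.7%; (0.5519 + 0.15)/0.2550 = 2.75, giving 0.3%; total 6.0%.

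Simulating the Wilcoxon test itself with the planned split (20,000 null trials per setting) agrees:

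| Assumed age shift d | Wilcoxon, two-sided | Wilcoxon, favouring guselkumab |
|---|---|---|
| 0 | 4.8% | 2.5% |
| 0.5 SD | 5.3% | 4.2% |
| 1 SD | 6.1% | 5.7% |

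Repeat runs ranged from 4.8% to 5.4% two-sided at d = 0.5 and from 5.7% to 6.1% at d = 1. The same test stratified by age stayed at about 5% two-sided and 2.5% in each direction. If adolescents improved less than children (d negative), the shift would favour placebo by the same amount.

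**Scale against the expected effect.** On a latent normal scale, 65% vs 13% is 0.385 − (−1.126) = 1.51 SD. The shift of 0.075 to 0.15 SD is 5% to 10% of that. With a true effect of 1.5 SD, the stratified and unstratified tests both rejected in every simulated trial.

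**Residual missing values.** No rate is given. If 0% to 20% of participants were still missing at Week 16 after the failure and rescue rules (an assumption), the test would use between 40 vs 25 and 32 vs 20 participants.

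**The case against.** The case for leaving the test alone has real substance.

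- **A rank test is a reasonable choice.** Percent improvement is capped at 100%. The adult trials described in Protocol 2.2.1 had PASI 90 rates of 73.3% and 70.0% on guselkumab, so values bunching near the ceiling in one group can be foreseen. The non-parametric clause in SAP section 5 covers that case, although 5.5.2.1.2.1 does not cite it. This stands, and it is why MMRM should not simply replace the rank test. It does not explain the missing strata, because a stratified rank test exists.
- **A reader might infer that the SAP breaches the protocol.** The documents do not support that. For this endpoint the protocol plans only a summary, and it leaves specific details to the SAP. The tension is with the protocol's generic wording on continuous parameters.
- **A reader might infer that the test has no missing-data handling.** That is also too strong. Treatment failures and rescue users are set to zero and kept in the test. Only residual missing values drop out, and no bias from them can be shown.
- **The age shift is assumed.** No document gives an age effect, and one of 0.5 to 1 SD that also acts on placebo may be generous. This stands.
- **No decision rests on the test.** PASI 50, 75, 90 and 100 are all compared with stratified tests and exact intervals. This stands.

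**Conclusion.** The point holds as a modest, specific gap. The one between-group test on continuous PASI leaves out the factor that the design itself ties to treatment, and the SAP gives no reason. Under an assumed age shift of 0.5 to 1 SD favouring adolescents, the two-sided error is about 5.3% to 6.1%. False results favouring guselkumab rise from 2.5% to about 4.2% to 5.7%. These figures rest on a normal outcome, the planned group sizes and an age effect that the documents do not supply. With no age effect there is no inflation.

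The p-value is nominal and lies outside the fixed testing sequence, so the co-primary and major secondary conclusions do not change. The choice of a rank test is not itself a fault.

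**What to change.** In SAP 5.5.2.1.2.1, replace the Wilcoxon rank-sum test with a van Elteren (stratified Wilcoxon) test stratified by age group and pooled region. State in advance that it falls back to age group alone if strata are too sparse: 10 vs 10 children split over two regions leaves small cells. Cite the non-parametric clause in SAP section 5 as the reason for departing from the MMRM rule in 5.5.2.1.

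Add the MMRM of SAP 5.5.2.1 as a supporting analysis and report the LS-mean difference with its 95% CI. This supplies the missing effect estimate. It also uses the earlier visits of participants without a Week 16 value, whom the rank test still drops. It should remain supporting because it assumes normality for a capped percentage.

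The cost is a wording change and a small amount of programming. Sample size, visits and the testing sequence are untouched. With no age effect, stratifying costs little power: in simulation at a 0.7 SD effect, 72.5% against 74.7% unstratified.

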5.5.2.1.3. Analyses Related to CDLQI, FDLQI, and BSA

5.5.2.1.3.1. Through Week 16

- The proportion of subjects achieving a CDLQI of 0 or 1 will be summarized at Week 8 and Week 16 among randomized participants with a baseline CDLQI > 1. The proportion of subjects with CDLQI of 0 or 1 at Week 16 will be compared between the guselkumab group and the placebo group using Fisher's exact test stratified by pooled region and age group.
- The change from baseline in CDLQI total score will be summarized at Week 8 and Week 16.

- The change from baseline in each CDLQI component score will be summarized at Week 16.
- The proportion of subjects achieving a FDLQI of 0 or 1 will be summarized at Week 8 and Week 16 among randomized subjects with a baseline FDLQI > 1. The proportion of subjects with FDLQI of 0 or 1 at Week 16 will be compared between the guselkumab group and the placebo group using Fisher's exact test stratified by region and age group.
- The change from baseline in FDLQI total score will be summarized at Week 8 and Week 16. The change from baseline in FDLQI at Week 16 will be compared between the guselkumab group and the placebo group using a Mixed Model for Repeated Measures (MMRM) model to test the difference between treatment groups and adjust for missing data.
- The change from baseline in each FDLQI component score will be summarized at Week 16.
- The change from baseline in BSA at Week 16 will be compared between the guselkumab group and the placebo group using a MMRM model.
- BSA involved and change from baseline in BSA will be summarized over time through Week 16.

In addition, relevant comparisons for secondary analyses at Week 16 will also be conducted between the etanercept group and the placebo group.

5.5.2.1.3.2. From Week 16 through Week 52

PASI 90 responders at Week 16 (after withdrawal of guselkumab)

- CDLQI score will be summarized at Week 16 and Week 28 for subjects randomized to the guselkumab group who were PASI 90 responder at Week 16, and were withdrawn from study agent at Week 16. Subjects who were retreated with guselkumab prior to Week 28 will be excluded.
- FDLQI score will be summarized at Week 16 and Week 28 for subjects randomized to the guselkumab group who were PASI 90 responder at Week 16, and were withdrawn from study agent at Week 16. Subjects who were retreated with guselkumab prior to Week 28 will be excluded.
- BSA involved and change from baseline in BSA will be summarized From Week 16 through Week 52 for subjects randomized to the guselkumab group who were PASI 90 responders at Week 16. BSA score at the time of retreatment will be carried forward after retreatment of guselkumab through Week 52.

PASI 90 responders at Week 16 (after retreatment guselkumab)

- The average duration of retreatment with guselkumab, CDLQI score at the time of retreatment, and CDLQI score at Week 52 will be summarized for subjects randomized to the guselkumab group who were PASI 90 responder at Week 16 and retreated prior to Week 52.
- FDLQI score at the time of retreatment, and FDLQI score at Week 52 will be summarized for subjects randomized to the guselkumab group who were PASI 90 responder at Week 16 and retreated prior to Week 52.

- BSA involved and change from baseline in BSA will be summarized at the time of retreatment and over time (eg, 4 weeks after retreatment, 8 weeks after retreatment, 12 weeks after retreatment) following retreatment with guselkumab.

PASI 90 non-responders at Week 16

- The proportion of participants achieving a CDLQI of 0 or 1 will be summarized over time through Week 52 among randomized subjects who were PASI 90 non-responder at Week 16 and with a baseline CDLQI>1.
- The change from baseline in CDLQI total score will be summarized over time through Week 52.
- The change from baseline in each CDLQI component score will be summarized at Week 52.
- The proportion of participants achieving a FDLQI of 0 or 1 will be summarized over time through Week 52 among randomized subjects who were PASI 90 non-responder at Week 16 and with a baseline FDLQI>1.
- The change from baseline in FDLQI total score will be summarized over time through Week 52.
- BSA involved and change from baseline in BSA will be summarized over time through Week 52.

5.5.2.2. Secondary Analyses for Participants Enrolled in Part 2

Efficacy analyses will be summarized for full analysis set in Part 2

- The proportion of PASI responses (PASI 50, 75, 90, and 100) will be summarized over time through Week 52.
- The proportions of subjects achieving an IGA score of cleared (0); an IGA score of cleared (0) or minimal (1); and an IGA score of mild or better (≤ 2) will be summarized over time through Week 52.
- The percent improvement from baseline in PASI will be summarized over through Week 52.
- BSA involved and change from baseline in BSA will be summarized over time through Week 52.
- The proportion of participants achieving an CDLQI of 0 or 1 will be summarized over time through Week 52 among participants with a baseline CDLQI>1.
- The change from baseline in CDLQI score will be summarized over time through Week 52.
-
- The proportion of participants achieving an FDLQI of 0 or 1 will be summarized over time through Week 52 among participants with a baseline FDLQI>1.
- The change from baseline in FDLQI score will be summarized over time through Week 52.

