**Footnotes:**

- a. The screening visit should occur within approximately 10 weeks before the Week 0 visit.
- b. Participants randomized to guselkumab or placebo who are PASI 90 responders at Week 16 will be withdrawn from treatment. Upon loss of  $\geq 50\%$  of the improvement in PASI achieved at Week 16, these participants will initiate guselkumab, followed by a second dose 4 weeks later followed by q8w administration through Week 52.
- c. A participant who discontinues study intervention but does not terminate study participation will continue to return for protocol-specified procedures and evaluations for at least 12 weeks following the last dose of study intervention (see Section 7.1) and complete all procedures and evaluations listed under the Study Termination Visit at the final visit. If a participant discontinues study intervention and terminates study participation, the procedures and evaluations for the Study Termination Visit should be performed at the last visit (Section 7.2).
- d. Participants who choose not to continue in the long-term extension of this study will not receive any administration of study intervention at Week 52 and will be asked to return for a study termination visit 12 weeks after their last administration of study intervention.
- e. All study procedures and evaluations are to be completed before study intervention administration.
- f. Must be signed before first study-related activity.
- g. Participants randomized to guselkumab who are PASI 90 nonresponders at Week 16 will receive a placebo injection at Week 16 to maintain the blind and continue guselkumab q8w dose regimen from Week 20 through Week 52.
- h. Participants randomized to placebo who are PASI 90 nonresponders at Week 16 will initiate guselkumab at Week 16 and Week 20 followed by q8w administration through Week 52.

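### The Week 16 and Week 28 CDLQI and FDLQI summary after withdrawal leaves out participants retreated before Week 28, so it describes a group selected on the outcome of withdrawal

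*SAP*

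**What the plan says.** SAP Section 5.5.2.1 sets the handling for participants randomised to guselkumab who were PASI 90 responders at Week 16 and were withdrawn. For responder variables: "Non-responder status will be assigned after retreatment for binary endpoints". For scores: "The measurement at the time of retreatment will be carried forward after retreatment for continuous endpoints".

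The instrument-specific sections mostly repeat this. IGA responses (5.5.2.1.1.2) and PASI responses (5.5.2.1.2.2) are set to non-response after retreatment. For PASI percent improvement the text is "PASI score at the time of retreatment will be carried forward after retreatment of guselkumab through Week 52", and for BSA, in the same subsection as the quality-of-life scores, "BSA score at the time of retreatment will be carried forward after retreatment of guselkumab through Week 52".

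CDLQI and FDLQI are treated differently. Section 5.5.2.1.3.2 summarises each score at Week 16 and Week 28 and then states, for each: "Subjects who were retreated with guselkumab prior to Week 28 will be excluded". No reason is given. Participants who are retreated appear in a separate item of the same section: "CDLQI score at the time of retreatment, and CDLQI score at Week 52 will be summarized for subjects randomized to the guselkumab group". FDLQI has a matching item.

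**The concern.** The Part 1 Schedule of Activities (Protocol 1.3.1, footnote b) gives the retreatment trigger: "Upon loss of $\geq 50\%$ of the improvement in PASI achieved at Week 16, these participants will initiate guselkumab". Anyone retreated before Week 28 has therefore done badly off drug by the study's own criterion. Removing them conditions the summary on the result of withdrawal. As written, the exclusion applies to the whole summary, so the same people leave the Week 16 column as well as the Week 28 column. Nothing requires the number removed to be shown.

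Effects on quality of life and maintenance of response after withdrawal are both secondary objectives. PASI and BSA will be reported for all withdrawn responders, and CDLQI and FDLQI for a favourable subset. A reader who sets the tables side by side could conclude that quality of life holds up better than skin disease, when part of the contrast comes from the denominators.

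**Working it through.** The plan states no figure for this analysis, so there is none to reproduce. The check compares rules, reads the visit schedule and adds an illustration.

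**1. Does the carry-forward rule cover CDLQI?** Yes. SAP Section 5 names it as the example of a continuous parameter: "Continuous response parameters (i.e. change from baseline in CDLQI) will be compared using Mixed Model Repeat Measurement (MMRM) analysis". The exclusion is therefore a departure from Section 5.5.2.1.

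**2. Who is excluded?** After Week 16, Part 1 visits are every 4 weeks, so retreatment before Week 28 would normally fall at Week 20 or Week 24. Participants who first meet the criterion at Week 28 stay in: they are retreated at that visit, and footnote e to the schedule puts all evaluations before dosing. Those who lost PASI 90 but less than half of their improvement also stay in.

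**3. Is there a score to carry forward?** Reading the CDLQI and FDLQI rows of the schedule by column position, both are collected at Weeks 0, 8, 16, 28, 36, 48, 52 and termination. Neither is collected at Week 20 or 24. The last scheduled score for an excluded participant is Week 16, taken while in PASI 90 response. Carrying it forward would also flatter the result. PASI, IGA and BSA are collected at every visit, so the rule works for them.

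**4. Does another table recover these participants at Week 28?** No. The separate item reports scores at retreatment and at Week 52. The first is normally not scheduled for someone retreated at Week 20 or 24, and the second is on treatment again.

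**5. Illustration of size.** Inputs:
- about 40 participants randomised to guselkumab (SAP 1.4);
- adult Week 16 PASI 90 rates of 70.0% and 73.3% (Protocol 2.2.1), giving 40 × 0.700 = 28.0 and 40 × 0.733 = 29.3 withdrawn; 28 is used below;
- share retreated before Week 28, *f*: not in the documents, assumed 5% to 40%;
- how much worse their CDLQI would be, *d*: not in the documents, assumed 3 to 8 points.

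If the retained group has mean *m*, the mean over all withdrawn is (1 − *f*)*m* + *f*(*m* + *d*) = *m* + *fd*. The summary as written looks better by *fd*.

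| *f* | Excluded (28*f*) | Remaining | *fd*, *d*=3 | *fd*, *d*=5 | *fd*, *d*=8 |
|---|---|---|---|---|---|
| 5% | 1.4 | 26.6 | 0.15 | 0.25 | 0.40 |
| 10% | 2.8 | 25.2 | 0.30 | 0.50 | 0.80 |
| 20% | 5.6 | 22.4 | 0.60 | 1.00 | 1.60 |
| 30% | 8.4 | 19.6 | 0.90 | 1.50 | 2.40 |
| 40% | 11.2 | 16.8 | 1.20 | 2.00 | 3.20 |

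These shifts show what the selection could conceal. No re-analysis can recover them, because the scores at relapse are not scheduled.

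**6. What a responder summary would do.** If a proportion *p* of those not retreated score 0 or 1, the proportion over all withdrawn, with retreated participants counted as non-responders, is (1 − *f*)*p*. That is 0.95*p* at *f* = 5% and 0.60*p* at *f* = 40%, assuming the same *f* among those with a baseline score above 1. It needs no score at Week 20 or 24.

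**The case against.** The strongest reply is that the different handling follows the data collected. With no CDLQI or FDLQI at Week 20 or 24, carry-forward has nothing suitable to carry, and excluding these participants is an open way to describe quality of life while still off drug. This stands as a likely explanation, although the SAP does not give it. It also rules out the simple remedy of deleting the exclusion and applying Section 5.5.2.1 to the mean.

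Other limits also stand. The summary is descriptive, untested and outside the fixed sequence. CDLQI after withdrawal is not among the protocol's listed endpoints; the listed withdrawal endpoints are the PASI times to loss of response, which this rule does not touch. Retreatment itself is visible through the cumulative incidence analysis in Section 5.5.2.1.2.2.

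Three stronger readings are tempting but not supported:
- *The table covers only participants who did not relapse.* Some who lost response remain in it (step 2).
- *The SAP breaches its own non-responder rule.* That rule is for binary endpoints, and no binary CDLQI or FDLQI endpoint is planned in withdrawn responders. Only the continuous rule is departed from.
- *Retreated participants are hidden.* They are summarised separately, though not at Week 28.

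The objection does not answer the selection itself. An openly stated exclusion still conditions on the outcome of withdrawal, and the population and the number removed are not required beside the result.

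**Conclusion.** The point holds in limited form. The Week 16 and Week 28 CDLQI and FDLQI summaries describe participants not retreated before Week 28, which is an outcome-selected subset of withdrawn responders, and they depart without explanation from the rule that IGA, PASI and BSA follow. The direction is expected to be favourable, on the assumption that participants who lose at least half of their PASI improvement have worse quality of life. The size is unknown: illustratively 0.15 to 3.2 CDLQI points, resting on assumed values for both the share retreated and their excess score. Primary and major secondary conclusions are unaffected. This is a cheap improvement to a descriptive analysis.

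**What to change.** In SAP Section 5.5.2.1.3.2:

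1. Add the proportion with CDLQI 0 or 1, and separately FDLQI 0 or 1, at Week 28 among all withdrawn guselkumab PASI 90 responders with a baseline score above 1. Count those retreated before Week 28 as non-responders under Section 5.5.2.1. The threshold and baseline restriction are already used at Week 16 in Section 5.5.2.1.3.1.
2. If the mean scores are kept, label the population *participants not retreated before Week 28*, show the numbers withdrawn and excluded, and give Week 16 scores for all withdrawn responders. State that the handling departs from Section 5.5.2.1 and why.
3. In the same edit, define which CDLQI or FDLQI record counts as the score at retreatment when none was scheduled at that visit.

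The cost is some wording and one extra descriptive table, with no new data. The figure will probably be less favourable. The main drawback is that a PASI-based trigger then sets quality-of-life non-response, so a retreated participant who scores 0 or 1 at Week 28 counts as a failure; the table footnote should say so.
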